2.4.2 Handling of missing data

In general, the number of subjects with missing values will be summarized and reported as appropriate in all outputs. The primary analysis will be performed using multiple imputation (MI) as the primary imputation method and repeated using baseline observation carried forward (BOCF) as a sensitivity analysis for missing values. With the BOCF imputation method, if a subject is missing their Month 1 GL-ILA/GL-SLA scores or LCL-ILA/LCL-SLA Month 1 scores, their score at baseline will be used, respectively.

The imputation using MI will assume the Missing Completely at Random (MCAR) missing data assumption. Regardless of the actual pattern of missing data, the Markov Chain Monte Carlo (MCMC) method of the MI procedure from the SAS® system will first be used to create a monotonic pattern of missing data. Then, a second MI procedure will be used to generate five sets of data with missing values imputed from observed data. Linear regressions will be employed to model the missing GL-ILA, GL-SLA, left LCL-ILA, right LCL-ILA, left LCL-SLA, and right LCL-SLA scores separately, with the following covariates included in each imputation model: treatment group and non-missing ILA or SLA data, respectively for GL and LCL, from earlier timepoints (baseline, Day 7, and Day 14). The imputed datasets will be used to create the composite responder variable, which will then be analyzed using the methodology described for the primary analysis of responder rates at Month 1 ([Section 2.4.3](#)). The results from the analysis of the multiple imputed datasets will be combined by the MIANALYZE procedure of the SAS® system. The seed number to be used will be the number 110197.

The secondary efficacy analysis (described in [Section 2.4.4](#)) will be performed using the Observed Cases (OC), that is, no imputation will be done. **CCI**

	Title 43QMI902 Statistical Analysis Plan US - QM1114-DP - GL&LCL	Doc id MA-43265
--	---	----------------------------------

CCI

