2.4.3 Primary analysis

The primary efficacy endpoints will be the composite responder rate based on the GL-ILA and GL-SLA of GL severity at maximum frown at Month 1 (described in [Section 1.3.3](#) and [Section 1.3.4](#), respectively) as well as the composite responder rate based on the LCL-ILA and LCL-SLA of LCL severity at maximum smile at Month 1 (described in [Section 1.3.1](#) and [Section 1.3.2](#), respectively). To evaluate the effectiveness of QM1114-DP versus placebo in the treatment of moderate to severe LCL and GL, alone or in combination, the responder rates of the QM1114-DP and placebo will be compared using the Cochran-Mantel-Haenszel (CMH) test stratified by site at the 5% significance level (2-sided). The group treated in one rhytid area alone (the QM1114-DP in LCL/placebo in GL; the placebo in LCL/QM1114-DP in GL treatment groups) and the group with concurrent LCL and GL treatment (the QM1114-DP in LCL/QM1114-DP in GL treatment group) will be analyzed separately.

The null hypothesis of no relationship between treatment and responder rate will be tested against the alternative hypothesis that there is a relationship between treatment and responder rate. For a significant result, the two-sided p-value of the comparison of the composite GL-ILA/GL-SLA and composite LCL-ILA/LCL-SLA responder rates between the QM1114-DP treated and placebo treated subjects at Month 1 using the CMH test needs to be smaller than 0.05. The Breslow-Day test will be used to assess the homogeneity of the odds ratios across all sites.

To control the type I error rate among the 4 primary efficacy comparisons, the fixed sequence procedure will be used which requires no adjustment to the level of significance. The comparisons will be done in the following order:

1. GL alone group vs placebo on the **GL scale** (i.e. the placebo in LCL/QM1114-DP in GL group vs. the placebo in LCL/placebo in GL group)
2. GL + LCL group vs placebo on the **GL scale** (i.e. the QM1114-DP in LCL/QM1114-DP in GL group vs. the placebo in LCL/placebo in GL group)
3. LCL alone group vs placebo on the **LCL scale** (i.e. the QM1114-DP in LCL/placebo in GL group vs. the placebo in LCL/placebo in GL group)
4. GL + LCL group vs placebo on the **LCL scale** (i.e. the QM1114-DP in LCL/QM1114-DP in GL group vs. the placebo in LCL/placebo in GL group)

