The estimates of the composite GL-ILA/GL-SLA and the composite LCL-ILA/LCL-SLA responder rates in each treatment group will be presented as well as the difference in responder rates (QM1114-DP responder rate – placebo responder rate). Corresponding 95% CI for the treatment group composite GL-ILA/GL-SLA and the LCL-ILA/LCL-SLA responder rates and the difference in responder rates along with the p-value for the difference will also be presented. The normal approximation (Wald) method will be used to calculate both the 95% CI for the individual treatment group composite GL-ILA/GL-SLA and LCL-ILA/LCL-SLA responder rates and the 95% CI for the difference in responder rates. The above responder rates will be presented in figures by visit and treatment group.

 GALDERMA	Title 43QMI902 Statistical Analysis Plan US - QM1114-DP - GL&LCL	Doc id MA-43265
--	---	----------------------------------

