2.7.3 Sample size calculation

The study is planned to include approximately 350 subjects in the mITT population: 100 subjects will be treated with QM1114-DP, 200 subjects will be treated with QM1114-DP and placebo, and 50 subjects will be treated with placebo.

The sample size is determined by the number of subjects exposed to QM1114-DP in the LCL and GL, and amount of long-term safety data.

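### Five imputations leave small but avoidable Monte Carlo noise in the primary difference and its confidence limits; about 100 would remove most of it for minutes of computing

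*SAP*

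**What the plan says.** SAP 2.4.2 states: "The primary analysis will be performed using multiple imputation (MI) as the primary imputation method". Baseline observation carried forward is the sensitivity analysis. Imputation has two steps. An MCMC step first makes the missing-data pattern monotone. A second step then uses linear regressions to "generate five sets of data with missing values imputed from observed data". The covariates are treatment group and the earlier scores on the same scale, from baseline, Day 7 and Day 14. On pooling: "The results from the analysis of the multiple imputed datasets will be combined by the MIANALYZE procedure of the SAS® system". On the seed: "The seed number to be used will be the number 110197".

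SAP 2.4.3 reports responder rates, differences, 95% limits and p-values. For the intervals, "The normal approximation (Wald) method will be used to calculate both the 95% CI" of each rate and of the difference. SAP 4.1 lists the primary tables and most Month 1 subgroup tables as MI on the mITT.

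Neither document justifies five, sets a Monte Carlo error target, gives an expected missing fraction, or raises the number elsewhere. The SAP does not say how many sets the MCMC step produces; five is attached only to the second step.

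**The concern.** A multiply imputed estimate has a component that depends only on the random draws. With five sets that component can show in the first decimal place of the reported difference and limits. A fixed seed makes one run repeatable but does not make the figure stable. An independent programmer whose code or record order differs could print visibly different limits from the same data.

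Missing Month 1 data matter here. Protocol 12.1 attributes the move from BOCF to MI as primary method to more drop-outs and missing data at that visit. Subjects assessed remotely at Month 1 are excluded from the mITT, so the imputed subjects are only those within the mITT who lack Month 1 scores.

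At stake is the precision of the printed primary result and, to a greater degree, of the subgroup tables. The noise scales with one over the square root of the sample size, so a subgroup a quarter of the size has about twice the noise.

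**Working it through.** **Inputs from the documents**
- Number of imputations m = 5, seed 110197, pooling by MIANALYZE (SAP 2.4.2).
- mITT size (SAP 2.7.3): "The study is planned to include approximately 350 subjects in the mITT population".
- Allocation 2:2:2:1 (SAP 1.1.2).

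**Reproducing the plan's figures.** 350 × 2/7 = 100 and 350 × 1/7 = 50; 413 × 2/7 = 118 and 413 × 1/7 = 59. These agree with the plan. Each primary comparison in the mITT is therefore 100 active vs 50 placebo. The plan states no Monte Carlo figure to reproduce.

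**Assumptions, because the documents give no values.** Missing fraction f of 2%, 5%, 10% and 15%. Responder rates of 60% vs 2%, with 40% vs 5%, 25% vs 5% and 20% vs 5% as alternatives. No predictive information from earlier scores, which makes the results upper bounds for the given rates and f.

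**Formulas**
- Complete-data variance of the difference: V = p1(1−p1)/100 + p0(1−p0)/50.
- Between-imputation variance: B = V × f/(1−f).
- Seed-to-seed SD of the pooled difference: √(B/m).

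**Numbers for 60% vs 2%.** V = 0.24/100 + 0.0196/50 = 0.002792, so the standard error is 5.28 points. At f = 10%, B = 0.002792 × 0.10/0.90 = 0.000310. With m = 5, √(0.000310/5) = 0.0079, or 0.79 points. With m = 100 it is 0.18 points.

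Seed-to-seed SD of the difference, percentage points:

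| Missing | m = 5 | m = 20 | m = 50 | m = 100 |
|---|---|---|---|---|
| 2% | 0.34 | 0.17 | 0.11 | 0.08 |
| 5% | 0.54 | 0.27 | 0.17 | 0.12 |
| 10% | 0.79 | 0.39 | 0.25 | 0.18 |
| 15% | 0.99 | 0.50 | 0.31 | 0.22 |

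Relative to the standard error, m = 5 gives 0.34/5.28 = 6% up to 0.99/5.28 = 19%. Going from 5 to 100 divides the noise by √20, about 4.5. The size hardly depends on the rates: at 40% vs 5% the m = 5 values are 0.37, 0.59, 0.86 and 1.09.

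**Simulation check.** The observed data were held fixed and only the seed varied (4,000 to 10,000 seeds per setting), with Rubin's rules. Central 95% ranges over seeds, 60% vs 2%, m = 5:

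| Missing | Difference | Lower 95% limit |
|---|---|---|
| 2% | 57.4 to 58.8% | 46.6 to 48.4% |
| 5% | 56.8 to 58.8% | 45.6 to 48.3% |
| 10% | 56.0 to 59.2% | 43.9 to 48.5% |
| 15% | 55.2 to 59.4% | 42.0 to 48.3% |

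With m = 100 the lower limit ranges over 46.9 to 47.5% at 5% missing and 46.1 to 47.1% at 10%.

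**Significance.** It never changed with the seed at 60% vs 2% or 40% vs 5%. With m = 5 it was lost in 1.6% of seeds at 20% vs 5% with 15% missing, and in 0.02% at 20% vs 5% with 10% missing and at 25% vs 5% with 15% missing. It was never lost with m of 20 or more.

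**The case against.** The strongest reply is that five is enough. The between-imputation variance has only 4 degrees of freedom, from which a reader might infer that the intervals or tests are unsound. They are not made so by the choice of five. Rubin's rules already include the B/m term, and the reference degrees of freedom are (m−1)(1+1/r)², with r = (1+1/m)B/V = 1.2 × f/(1−f). That gives about 1,133, 289 and 131 at 5%, 10% and 15% missing, hence t multipliers of 1.962 to 1.978 against 1.960. The expected standard error rises only from 5.42 to 5.45, from 5.57 to 5.63 and from 5.73 to 5.82 points compared with unlimited imputations. This part of the reply stands: average precision is nearly full. It does not say how far one printed limit moves between seeds.

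A reader might also infer that the result cannot be reproduced, or that the seed could be chosen to suit. The prespecified seed rules out both. Seed-free BOCF and observed-case analyses on the mITT are planned as well.

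Finally, the figures rest on assumed rates and missingness, and Day 7 and Day 14 scores would shrink them by an amount the documents do not allow us to state. That also stands, which is why they are given as upper bounds over a range.

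**Conclusion.** The point holds as a minor one. The plan uses five imputations without giving a reason, and this leaves noise of up to about 0.3 to 1.0 points (SD) in the primary difference for 2% to 15% missing, against about 0.1 to 0.2 points with 100. The lower limit moves more than the difference does. These values assume 60% vs 2% responders, 100 vs 50 subjects and no information from earlier scores; with no missing Month 1 data in the mITT the noise is zero.

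The stronger reading, that the trial's conclusion hangs on the seed, is not supported. Significance changed only when a small assumed effect was combined with 10% or 15% missingness, and then in at most 1.6% of seeds. The gain from more imputations is a steadier printed estimate and interval.

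**What to change.** In SAP 2.4.2, raise the number of imputations from five to about 100, and to no fewer than 50. State the number for both steps, so that the MCMC monotone step and the regression step carry it consistently; changing the word in the second step alone leaves the first unspecified. Keep seed 110197. Report the Monte Carlo error of the pooled difference, √(B/m), beside the primary result. The imputation covariates, test, population and visits stay as they are. The cost is a short SAP edit and minutes of computing.

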1.3.1 Investigator 4-point Photographic Scale of Lateral Canthal Line Severity (LCL-ILA)

The LCL-ILA is a 4-point validated scale for assessment of lateral canthal lines ([Appendix A](#)). The validated LCL-ILA, developed by Galderma, includes two grading systems: one for the Investigator live assessments at maximum smile, **CCI**

CCI. The scale represents LCL severities from none (grade 0), mild (grade 1), moderate (grade 2), to severe (grade 3). Each grade is also depicted by an individual photograph and descriptive text.

The Investigators will use the LCL-ILA for direct, live comparison with the subject's face at

CCI maximum smile. Left and right LCL should be assessed separately at **CCI**

maximum smile. The Investigator will perform the LCL-ILA at:

- Screening/Baseline (prior to treatment) visit(s)
- all post-treatment visits.

Multiple responder indicators will need to be created as follows:

- For the co-primary LCL endpoint, LCL-ILA indicator: subjects that achieved a score of 0 or 1, and had at least 2 grade improvement from baseline at maximum smile at Month 1, for both left and right LCL, will have the value '1'. This indicator will be used in combination with the primary endpoint LCL-SLA indicator to define the co-primary LCL endpoint composite responder.
- Subjects who achieve a score of 0 or 1 in the LCL-ILA at maximum smile, for both left and right LCL, at each respective post-baseline visit will be considered an LCL-ILA at maximum smile responder for that visit

CCI

- Subjects that achieved at least 1 grade improvement from baseline in the LCL-ILA at maximum smile, for both left and right LCL, at a given post-baseline visit will be considered an LCL-ILA at maximum smile grade 1 improvement responder for that visit.

CCI

- Subjects that achieved at least 2 grade improvement from baseline in the LCL-ILA at maximum smile, for both left and right LCL, at a given post-baseline visit will be considered an LCL-ILA at maximum smile grade 2 improvement responder for that visit.

CCI

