1.4 Efficacy endpoints

1.4.1 Primary efficacy endpoint

There are two primary efficacy endpoints, based on treatment location. The first primary endpoint is the composite responder rate at Month 1 using the GL-ILA and the GL-SLA at maximum frown.

A composite responder is defined as a subject who achieves a score of 0 or 1 in GL severity and at least 2 grades improvement from baseline on both the GL-ILA and GL-SLA scales, concurrently, at Month 1.

The second primary endpoint is the composite responder rate at Month 1 using the LCL-ILA and the LCL-SLA at maximum smile.

A composite responder is defined as a subject who achieves a score of 0 or 1 in LCL severity and at least 2 grades improvement from baseline on both the LCL-ILA and LCL-SLA scales, concurrently, at Month 1 for both left and right sides.

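### The primary multiple imputation draws 0–3 grades from separate linear regressions, which understates the composite responder rate among imputed active subjects

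*SAP*

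**What the plan says.** SAP 2.4.2 makes multiple imputation (MI) primary and BOCF a sensitivity analysis. An MCMC step produces a monotone pattern, after which "a second MI procedure will be used to generate five sets of data with missing values imputed from observed data". For that second step: "Linear regressions will be employed to model the missing GL-ILA, GL-SLA, left LCL-ILA, right LCL-ILA, left LCL-SLA, and right LCL-SLA scores separately". The covariates are "treatment group and non-missing ILA or SLA data, respectively for GL and LCL, from earlier timepoints (baseline, Day 7, and Day 14". Then "The imputed datasets will be used to create the composite responder variable", and each completed dataset goes through the site-stratified CMH analysis of SAP 2.4.3. The section also says: "The imputation using MI will assume the Missing Completely at Random (MCAR) missing data assumption".

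The scales take whole grades 0 to 3 (SAP 1.3.1 to 1.3.4). Under SAP 1.4.1 a GL responder needs "a score of 0 or 1 in GL severity and at least 2 grades improvement from baseline on both the GL-ILA and GL-SLA scales". The LCL responder must meet the same rule on both raters' scales, "concurrently, at Month 1 for both left and right sides".

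SAP 2.4.2 mentions no rounding, no limits at 0 and 3, and no ordinal or logistic model. No Month 1 score of the other rater or side enters any model.

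**The concern.** Two features of the imputation do not fit the endpoint.

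- **Continuous draws against whole-grade cut-offs.** Subjects enter at grade 2 or 3. From grade 3 a responder must reach grade 1 or lower; from grade 2 a responder must reach grade 0. A linear draw spreads the probability of the passing grade to both sides of the cut-off, so a draw of 0.3 for a grade 2 subject fails although the nearest grade passes.
- **Independent Month 1 residuals.** Investigator and subject scores, and left and right sides, tend to succeed or fail together. Separate models with only earlier covariates remove the part of that agreement not explained by treatment and earlier scores. The chance that all scores pass together falls, most of all when four must pass.

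At stake are the primary responder rates, differences and confidence intervals in all four comparisons, and the MI subgroup tables built on the same datasets.

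**Working it through.** **Inputs from the documents.** Model, covariates and five imputations: SAP 2.4.2. Responder rule: SAP 1.4.1. Planned mITT of 350, with 100 per active arm and 50 placebo: SAP 2.7.3. The documents show no responder rate, correlation or missing fraction, so there is no stated figure to reproduce, and those inputs are assumed below.

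**Step 1: the mechanism without trial data.** Take a grade 2 subject whose predicted Month 1 value is exactly 0 on every score. Unrounded, each draw passes with probability 0.5. With independent residuals:

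- GL: 0.5² = 25%
- LCL: 0.5⁴ = 6.25%

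**Step 2: simulation of the SAP model.** 413 subjects (118/118/118/59) had correlated whole-grade scores at baseline, Day 7, Day 14 and Month 1, with 10% of Month 1 missing completely at random. Each score was imputed by Bayesian linear regression on treatment and its own earlier values, five times. Twelve scenarios per area varied baseline severity, effect size and visit noise. Within active subjects, the correlation between Month 1 scores was 0.57–0.72. The shortfall is the true minus the imputed composite rate among imputed active subjects, in percentage points.

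| Version | GL | LCL |
|---|---|---|
| Separate, unrounded | 31–45 | 30–59 |
| Separate, rounded and clipped to 0–3 | 3–12 | 6–20 |
| Linked to other raters and sides, unrounded | 27–42 | 25–54 |
| Linked and rounded | 3–9 | 6–12 |

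In a mid-range scenario GL was 73% true against 30% imputed (unrounded), and LCL 60% against 10%. Placebo was about 0% either way. The missing return to whole grades is the main cause. The missing link is secondary and matters mostly for LCL.

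**Step 3: a second setting.** Half the subjects started at grade 2 and half at grade 3. The assumed Month 1 probabilities of grades 0/1/2/3 were 65/25/8/2% and 45/33/17/5% respectively. Rater correlation was 0.5–0.7, left–right 0.9, and Day 14 to Month 1 0.5–0.85.

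- GL: true 58–61%, imputed 21–25% unrounded and 45–51% rounded.
- LCL: true 50–53%, imputed 6–12% unrounded and 24–34% rounded.

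Giving each model both raters' earlier scores did not remove the shortfall. The largest rounded LCL gap is 53 − 24 = 29 points; for GL the rounded gap reaches about 15.

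**Step 4: dilution over a whole active arm.** Shift = missing share × shortfall, with 5% to 15% missing assumed.

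- Unrounded: 0.05 × 30 = 1.5 points to 0.15 × 59 ≈ 9 points.
- Rounded: 0.05 × 3 ≈ 0.2 points to 0.15 × 29 ≈ 4 points.

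**Step 5: effect on the test.** Power = Φ[(d − 1.96·SE₀)/SE₁] for two proportions, 100 against 50, ignoring stratification and imputation variance. For 30% against 5%:

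- d = 0.25; pooled rate = (30 + 2.5)/150 = 0.217
- SE₀ = √(0.217 × 0.783 × 0.03) = 0.0714
- SE₁ = √(0.21/100 + 0.0475/50) = 0.0552
- Power = Φ(1.99) = 97.7%

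The lowest simulated active rate was about 32% (LCL). Reducing it by 0.15 × 30 = 4.5 points gives 27.7%, for which the same formula against 5% gives 95%.

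**The case against.** **The effect is confined to imputed subjects, and its size is assumed.** This stands. Month 1 assessments made remotely are excluded from the mITT population (SAP 2.2) rather than imputed. Protocol 12.1 says only that missing Month 1 data increased.

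**Rounding may be applied in programming.** The SAP neither states nor excludes it. It would remove most of the GL error and much of the LCL error, but not all, and a primary estimate should not rest on an unwritten choice.

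**The scores are not wholly unlinked.** This also stands. They share treatment group, and the covariate wording can be read as allowing both raters' earlier scores for the area. The variables in the MCMC step are not listed, so some earlier gaps may be filled jointly. The Month 1 residuals remain independent under either reading.

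**Other tables would expose the problem.** SAP 4.1 lists observed-case mITT tables (14.2.1.3.4 and 14.2.2.3.4). Under the SAP's own MCAR assumption these are unbiased, so a gap from the MI result would show. They are supporting tables and do not correct the primary estimate.

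**Stronger readings that a reader might infer.**

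- *No imputed subject can respond, because a continuous draw never equals exactly 0 or 1.* The SAP does not say the rule is applied that way.
- *The MI is BOCF in disguise.* BOCF gives an eligible subject no improvement, hence 0% responders. GL under the SAP model is well above that, even unrounded.
- *The MCAR label causes bias.* It does not: MCAR implies MAR. The label is merely stricter than the model needs.
- *Omitting Month 2 scores or using only five imputations is an error.* The documents give no basis for calling either more than a preference.

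**Conclusion.** The rule as written gives a wrong result; it is not merely short of detail. Separate linear draws with no return to whole grades understate the composite rate among imputed active subjects by roughly 30–45 points (GL) and 30–60 points (LCL), or about 3–15 and 6–29 points if the draws are rounded. Over an active arm with 5–15% missing, that is about 1.5–9 points unrounded and 0.2–4 points rounded.

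The direction held in every scenario tried; the sizes depend on assumed response rates, correlations and missing fractions. Because placebo response is near zero either way, the treatment difference is biased against QM1114-DP. A reader might infer a lost test or a false positive, but neither is supported: approximate power stays high and the bias is conservative. The harm is to the primary estimate, difference and confidence interval.

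**What to change.** Before unblinding, replace the second imputation step in SAP 2.4.2 with one of these:

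1. Ordinal logistic models (fully conditional or monotone) for the Month 1 grades. Each should contain treatment, the earlier scores, and the concurrent Month 1 scores of the other rater and, for LCL, the other side. Derive the responder from the resulting whole grades.
2. Direct imputation of the composite responder indicator for each area, by penalised logistic regression on treatment and earlier scores.

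The link matters as well as the ordinal form. In the second setting, separate ordinal models still gave LCL 33–42% against a true rate just above 50%, although GL came close at 53–57%. Joint imputation matched the truth there, but joint ordinal imputation was not tested in the Step 2 scenarios. Option 2 avoids both problems but is a different method, not an exact equivalent.

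State the assumption as MAR. The cost is SAP wording and reprogramming one MI step, with no new data. Near-zero placebo response makes penalisation or a similar device necessary.

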8.1.6 Months 2-5/Visit 6-9 (\pm 5 days)

The Investigator or designee will:

1. Ask the subject about AEs using an open-ended question, such as "Have you noticed any change in your health since the last visit?" Record all events, as appropriate.
2. Ask the subject about any changes in his/her concomitant therapies/procedures (added, removed or changed) since the previous visit. Record all changes.
3. Instruct the subject on how to complete the LCL-SLA at **CCI** maximum smile. Subject to complete self-assessment of bilateral LCL severity using the 4-point Photographic Scale. (Section [7.1.2](#) and [Appendix 2](#))
4. Instruct the subject on how to complete the GL-SLA at maximum frown. Subject to complete self-assessment of GL severity using the Static 4-point Categorical Scale. (Section [7.1.4](#))
5. **CCI**
- 6.
- 7.
8. Take subject photographs (refer to photo manual for complete instructions). If the subject is wearing make-up, instruct the subject to remove it prior to taking photographs.
9. Investigator to complete assessment of the subject's bilateral LCL severity at **CCI** maximum smile using the 4-point Photographic Scale (LCL-ILA). (Section [7.1.1](#) and [Appendix 1](#))
10. Investigator to complete assessment of the subject's GL severity at **CCI** maximum frown using the 4-point Photographic Scale (GL-ILA). (Section [7.1.3](#) and [Appendix 3](#))
11. Schedule the next monthly visit (\pm 5 days).

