Section 9.1.2.5, Imputation of Missing Data	Due to COVID-19 pandemic actions. An increased number of drop-outs/ missing data at Month 1 visit.	Primary imputation changed to “MI” instead of “BOCF”.
Section 9.1.5, Inferential Statistical Analyses	Clarification due to COVID-19 pandemic actions.	Added: “The analysis of the primary efficacy endpoint will be based on the mITT population. A sensitivity analysis of the primary efficacy endpoint will be performed using the ITT population.”
Section 9.2, Sample Size Determination	Clarification due to COVID-19 pandemic actions.	Clarification for increased number of subjects during the conduct of the study added. “The sample size is determined by the number of subjects exposed to QM1114-DP in the LCL and GL, and amount of long-term safety data.” was moved from Section 9.2.3 to Section 9.2
Synopsis and Section 9.2.1, Historical Data	Clarification due to COVID-19 pandemic actions.	Both the initially planned and the increased sample size included.
Section 9.2.3, Sample Size Calculation	Clarification due to COVID-19 pandemic actions.	Added: “... in the mITT population
Section 12: Section 12.1	Protocol Amendment	Added Section: Summary of Changes Protocol version 3.0 to version 4.0

 GALDERMA	Title 43QMI902 Clinical Study Protocol - QM1114 - LCL and GL	Doc id MA-40371
--	---	----------------------------------

[figure not shown]

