2.4.4 Secondary analysis

To evaluate the effectiveness of a single dose of QM1114-DP in the LCL and QM1114-DP in the GL, alone or in combination, the GL-ILA at maximum frown and LCL-ILA at maximum smile responders at each visit will be presented in frequency tables. The respective responder rates (specified in [Section 1.4.2](#)) will be calculated and presented by treatment group and visit. Corresponding 95% CI for the GL-ILA at maximum frown and LCL-ILA at maximum smile responder rates will also be presented. The Clopper-Pearson (Exact) method will be used to calculate the CIs. The CMH analyses, as outlined in the Section 2.4.3, will be conducted for descriptive purposes.

The secondary analysis will be based on the ITT population with the remote visit assessments excluded. A sensitivity analysis will be conducted using the ITT population including the remote visit assessments.

The above responder rates will be presented in figures by visit and treatment group.

Effective date: 2021-02-05 13:16

Effective

Version: 1.0

 GALDERMA	<small>Title</small> 43QMI902 Statistical Analysis Plan US - QMI114-DP - GL&LCL	<small>Doc id</small> MA-43265
---	--	-----------------------------------

CCI

 GALDERMA	Title 43QMI902 Statistical Analysis Plan US - QM1114-DP - GL&LCL	Doc id MA-43265
--	---	----------------------------------

CCI

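### The Month 1 imputation model leaves out the Month 2 ratings; adding them is a cheap, modest gain in accuracy and is not expected to change the primary test

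*SAP*

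**What the plan says.** SAP 2.4.2 makes multiple imputation the primary way of handling a missing Month 1 rating. The GL-ILA, GL-SLA and the left and right LCL-ILA and LCL-SLA scores are each modelled by linear regression. The covariates are treatment group and "non-missing ILA or SLA data, respectively for GL and LCL, from earlier timepoints (baseline, Day 7, and Day 14"). No later visit is named.

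The procedure has two steps. The MCMC method "will first be used to create a monotonic pattern of missing data", and then "a second MI procedure will be used to generate five sets of data". The variables entered in the first step are not listed. The stated assumption is the strongest one: "The imputation using MI will assume the Missing Completely at Random (MCAR) missing data assumption".

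Protocol 12.1 explains why MI replaced BOCF as the primary method: "An increased number of drop-outs/ missing data at Month 1 visit".

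Month 2 data will exist for anyone who attends. Protocol Table 2 schedules all four scales at every post-treatment visit. For Months 2 to 5, Protocol 8.1.6 includes, for example, "Subject to complete self-assessment of GL severity using the Static 4-point Categorical Scale". Protocol 6.1.7.3 provides for one treatment, at baseline, so a Month 2 rating reflects the same injection.

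The other planned versions of the primary analysis (SAP 2.4.3.1 and the table list in 4.1) are BOCF on the mITT, and observed cases on the ITT, mITT, PP and Safety populations. None uses Month 2 to inform Month 1.

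**The concern.** MI was brought in for gaps at Month 1. Some of those gaps may be intermittent, with the subject absent at Month 1 and present at Month 2. For such a subject the database holds a later rating on the same scale after the same injection, and the model ignores it.

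MI corrects for selective missingness only as far as the variables in the model explain it. Suppose a subject misses Month 1, shows no response at Month 2, and had a typical Day 7 and Day 14 for the arm. The model imputes that subject as a typical member of the arm. If such subjects miss Month 1 more often than responders do, the imputed responder rate is too high. What is at stake is the accuracy of the reported responder rates and of their difference.

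**Working it through.** **Inputs from the documents.** Month 1 is Day 28 and Month 2 is Day 56 (Protocol Table 2). The planned mITT is about 100 per active group and 50 placebo (SAP 2.7.3). There are five imputations (SAP 2.4.2).

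**Inputs not in the documents.** No between-visit correlation and no Month 1 missingness rate is given, and the responder-rate assumptions are redacted. The plan states no figure on this point that could be reproduced. Everything below is therefore a range under stated assumptions.

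**Step 1: who is affected.**

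| Month 1 status | Treatment in the primary analysis | Can Month 2 help? |
|---|---|---|
| Rated on site | Observed score used | Not needed |
| Rated remotely | Excluded from mITT (SAP 2.2) | No |
| Missing, dropped out | Imputed | No Month 2 score |
| Missing, returned at Month 2 | Imputed | Yes |

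Only the last row matters, and its size is unknown.

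**Step 2: precision under MCAR.** Let r be the correlation at a 28-day lag, assumed 0.4 to 0.8.

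- Exponential decay: R² of Month 1 on the earlier visits is r. With Month 2 added it is (r + r² − 2r³)/(1 − r³). For r = 0.6 this is (0.6 + 0.36 − 0.432)/(1 − 0.216) = 0.528/0.784 = 0.67.
- Compound symmetry with k ratings: R² = kr²/(1 + (k − 1)r). For r = 0.6, k = 3 gives 1.08/2.2 = 0.49 and k = 4 gives 1.44/2.8 = 0.51.

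| r | Decay: without → with Month 2 | Compound symmetry: without → with |
|---|---|---|
| 0.4 | 0.40 → 0.46 | 0.27 → 0.29 |
| 0.6 | 0.60 → 0.67 | 0.49 → 0.51 |
| 0.8 | 0.80 → 0.85 | 0.74 → 0.75 |

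With m the missing share, the variance of an arm mean is roughly proportional to 1 + [m/(1 − m)](1 − R²). For m = 0.15 and r = 0.6 under decay, m/(1 − m) = 0.176. The standard-error ratio is √[(1 + 0.176 × 0.400)/(1 + 0.176 × 0.327)] = √(1.0706/1.0576) = 1.006. Over m = 2% to 15% and both structures, leaving out Month 2 inflates the standard error by about 0.01% to 0.6%.

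**Step 3: bias when missingness follows later response.** This is a simulation on a latent normal scale with a 60% true response. Missingness is 6% in Month 2 responders and 18% in non-responders, so overall 0.60 × 6% + 0.40 × 18% = 10.8%. The assumed correlations (low / middle / high) are Day 14 with Month 1 at 0.50 / 0.60 / 0.65, and Month 1 with Month 2 at 0.60 / 0.70 / 0.80.

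| | Low | Middle | High |
|---|---|---|---|
| True rate among the missing | 49% | 47% | 44% |
| Imputed, SAP covariates | 57% | 55% | 54% |
| Imputed, Month 2 added | 49% | 47% | 44% |

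Arm-level bias is the missing share times the error among the missing. In the middle case, 0.108 × (55 − 47) = 0.9 points. The range is about 0.9 to 1.1 points, and about zero with Month 2.

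Those correlations make Month 2 the closer relative of Month 1. Reversing the middle case (0.70 for Day 14, 0.60 for Month 2) gives roughly 0.5 points, and exponential decay at 0.6 gives roughly 0.5 to 0.6.

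**Step 4: other mechanisms, same simulation.**

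- MCAR, or missingness driven by Day 14 response: essentially no bias from the SAP's model.
- Missingness driven by Month 1 itself: adding Month 2 reduces the bias only from 2.4 to 1.9, 2.1 to 1.8 or 1.8 to 1.6 points, depending on the correlations.

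**Step 5: the tested difference.** A separate simulation used 100 versus 50 subjects, 5% or 15% missing, and imputed scores rounded to 0–3 (a step the SAP does not specify). Adding Month 2 moved the estimated difference by at most about 0.001 under MCAR and 0.008 when missingness depended on the Month 2 score. This gives the size of the movement only. Both models fell below the complete-data difference, even under MCAR (for r = 0.4 and 15% missing: 0.516 complete, 0.499 without Month 2, 0.501 with). Imputing and rounding a bounded score thus has its own error there. When missingness followed Month 2, the model with Month 2 was the further of the two from the complete-data value (0.496 against 0.504, complete 0.514). The removal of bias in Step 3 therefore assumes that the imputation model is otherwise adequate.

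**The case against.** The strongest reply is that this is a refinement with almost no consequence. Under the SAP's MCAR assumption the omission causes no bias. The protocol attributes the missing data to the pandemic, which need not be related to response. If subjects stay away because they saw little change by Day 14, the model already conditions on that. Drop-outs gain nothing. BOCF on the mITT is much harsher than any shift seen here: carrying baseline forward gives zero improvement, so every imputed subject becomes a non-responder. With assumed rates of 40% to 70% on active and 1% to 10% on placebo, 100 versus 50 subjects gives power of at least 98.7%. All of this stands, and it limits the point to a cheap improvement.

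The reply does not show that the omission is right. MCAR cannot be verified, and neither BOCF nor the observed-case runs improve the primary estimate.

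The MCMC variable list is also unstated. If Month 2 were entered in that step, an intermittently missing Month 1 score could be informed by it. The text gives no sign of this, so it needs stating.

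Two stronger readings are tempting. First, a reader might infer that Month 2 is the best available predictor of Month 1. The documents give no correlations, and Day 14 is nearer in time (14 days against 28) and already in the model. Second, because "The secondary analysis will be based on the ITT population with the remote visit assessments excluded", a reader might infer that remote ratings are regarded as unfit for analysis and should not feed the imputation. The SAP keeps them in the ITT observed-case analysis, in the visit-type subgroup (2.4.3.2) and in the secondary sensitivity analysis (2.4.4). How remote Day 7, Day 14 or Month 2 ratings enter the model is an optional clarification.

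**Conclusion.** The point holds as a modest, inexpensive improvement. On its text, SAP 2.4.2 leaves out Month 2 ratings that will be available for mITT subjects who missed Month 1 and returned, and no planned analysis brings them in. Under MCAR the loss is a fraction of a percent of the standard error. If missingness follows later response, the arm-level rate could be biased by roughly 0.5 to 1 point. That rests on a 60% response, about 11% missing, all of those subjects returning at Month 2, and the assumed correlations. Month 2 then removes the bias when missingness follows Month 2 status, and only trims it when missingness depends on Month 1 itself.

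A reader might infer that the primary conclusion is at risk, or that most Month 1 gaps are intermittent. The documents support neither: they speak of drop-outs and missing data together without a rate, and the sizes above are not expected to change the primary test.

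**What to change.** In SAP 2.4.2:

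1. Add the Month 2 rating of the same scale as an auxiliary variable in each Month 1 imputation model. Use a joint (MCMC) or fully conditional specification, because a forward-only regression on earlier visits cannot use a later one.
2. List the variables entered in the MCMC step.
3. Optionally, say how remote Day 7, Day 14 and Month 2 ratings are handled in the model.

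If the primary model is to stay as written, pre-specifying the Month 2 version as a sensitivity analysis would be a smaller step.

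The cost is a few lines of SAP wording and code, with no new data. The downside is a slightly larger imputation model. The composite endpoint, CMH test, testing order and mITT population are unchanged.
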